6. ANALYSIS INTERPRETATION

All analyses are descriptive.

7. INTERIM ANALYSES

7.1. Sequence of analyses

Analyses to evaluate objectives and endpoints will be performed stepwise:

- Month 6: A first analysis will be performed on all reactogenicity, safety and immunogenicity data available and as clean as possible, when data for at least primary and secondary endpoints up to Month 6 are available for all participants. This analysis will be considered as final for those endpoints. *
- Month 13: A second analysis will be performed on all reactogenicity, safety and immunogenicity data available and as clean as possible, when data for at least primary and secondary endpoints up to Month 12 are available for all participants, as well as data up to 1 month after the first revaccination (Month 13) in the RSV_annual group. This analysis will be considered as final for those endpoints *.

- Month 18: A third analysis will be performed on all safety and/or immunogenicity data available and as clean as possible, when data for secondary endpoints up to Month 18 are available for all participants. This analysis will be considered as final for those endpoints *. Safety and immunogenicity analysis may be performed at different time depending on data availability.
- Month 25: A fourth analysis will be performed on all safety, reactogenicity and immunogenicity data available and as clean as possible, when data for at least primary and secondary endpoints up to Month 24 are available for all participants, as well as data up to 1 month after the second revaccination (Month 25) in the RSV_annual group and up to 1 month after the first revaccination (Month 25) in the RSV_flexible revaccination group. This analysis will be considered as final for those endpoints *.
- The final **End of Study** analysis will be performed when all reactogenicity, safety and immunogenicity data for at least primary and secondary endpoints up to study conclusion are available for all participants (Month 36).
- If the data for tertiary endpoints become available at a later stage, (an) additional analysis/analyses will be performed.
- *Each analysis can be considered as final, as it is based on data that is as clean as possible. However, the consecutive analysis of the same time point might slightly differ at the next analysis e.g when M6 data are re-analyzed at the time of M13 analysis. If major changes are identified, they will be described in the clinical study report.

Description	Analysis ID	Disclosure Purpose (CTRS=public posting, SR=study report, internal)
End of study analysis	E1_01	CTRS, SR
Analysis up to Month 6	E1_02	SR
Analysis up to Month 13	E1_03	CTRS, SR
Analysis up to Month 18	E1_04	Internal
Analysis up to Month 25	E1_05	Internal

7.2. Statistical considerations for interim analyses

All analyses will be conducted on final data (as clean as possible) and therefore no statistical adjustment for interim analyses is required.

8. CHANGES TO THE PROTOCOL DEFINED STATISTICAL ANALYSIS

This statistical analysis plan complements the analyses described in the protocol.

The changes compared to the planned statistical analysis specified in the Protocol amendment 1 (Dated: 01 April 2022) are described below:

• The number and percentage of participants with at least one administration site event (solicited only), with at least one systemic event (solicited only) and with any solicited event during the 4-day follow-up period after vaccination

- Related SAEs/pIMDs and Fatal SAEs will be tabulated after each dose.
- SAEs/pIMDs within 30 days following each vaccination.

9. NON-STANDARD DATA DERIVATION RULES AND STATISTICAL METHODS

The following sections describe additional derivation rules and statistical methods which are not presented in Section 10.1 (Business rules for standard data derivations and statistical methods).

9.1. Handling of missing data

9.1.1. Dates

When partially completed dates (i.e. with missing day or month) are used in calculations, the following rules will be applied:

- AE start dates with missing day:
 - If the month is not the same as the vaccine dose, then the imputed start date will be the 1st of the month
 - If the event starts in the same month as the vaccine dose, the flag indicating if the event occurred before or after vaccination (AE.AESTRTPT) will be used to complete the date. If 'after vaccination' is selected, the imputed start date will match the vaccine dose given during that month. If 'before vaccination' is selected, the imputed date will be one day before the vaccine dose given during that month.
- AE start dates with missing day and month:
 - If the year is not the same as the vaccine dose, then the imputed start date will be the 1st of January.
 - If the event starts in the same year as the vaccine dose, the flag indicating if the event occurred before or after vaccination (AE.AESTRTPT) will be used to complete the date. If 'after vaccination' is selected, the imputed start date will match the first vaccine dose given during that year. If 'before vaccination' is selected, the imputed date will be one day before the first vaccine dose given during that year.
- AE end dates with missing day: the imputed end date will be the last day of the month (30 or 31) or the study conclusion date whichever comes first.
- AE end dates with missing day and month: the imputed end date will be the last day of the year (31st of December) or the study conclusion date whichever comes first.

All incomplete concomitant medication/vaccination start/end date will follow the rules above.

10. ANNEXES

10.1. Business rules for standard data derivations and statistical methods

This section contains standard rules for data display and derivation for clinical and epidemiological studies.

10.1.1. Attributing events to vaccine doses

The dose relative to an event is the most recent study dose given to a participant prior to the start of a given event. For example, if the start date of an AE is between Dose 1 and Dose 2, the relative dose will be Dose 1.

If an event starts on the same day as a study dose, the relative dose will be derived from the additional information provided in the case report form (CRF) using the contents of the flag indicating if the event occurred before or after study dose. If 'after vaccination is selected, the relative dose for the event will be the one administered on the start day of the event. If 'before vaccination is selected, the relative dose for the event will be the dose prior to this one.

10.1.2. Handling of missing data

10.1.2.1. Dates

When partially completed dates (i.e. dates missing a day and/or month) are used in calculations, the following standard rules will be applied:

- A missing day will be replaced by 15th
- A missing day and month will be replaced by June 30th.

See also exceptions in Section 9.1.

10.1.2.2. Laboratory data

Refer to Section 5.1.2 for more details.

10.1.2.3. Daily recording of solicited events

10.1.2.3.1. Studies with paper diaries

For studies using paper diaries which have questions in the CRF indicating the presence or absence of solicited events, the following rules are applicable:

• Denominators for the summary of administration site (or systemic) solicited events will be calculated using the number of participants who respond "Yes" or "No" to the question concerning the occurrence of administration site (or systemic) events.

- When a specific solicited event is marked as having not occurred following a specific study dose (i.e. SDTM CE.CEOCCUR=N for the specified post-dose period for the event in question), all daily measurements will be imputed as Grade 0.
- When a specific solicited event is marked as having occurred following a specific study dose (i.e. SDTM CE.CEOCCUR=Y for the specified post-dose period for the event in question), any missing daily recordings will be given imputed values to allow them to contribute to the 'Any' rows but not to specific grade rows of the solicited event summary tables.
- When the occurrence of a specific solicited event is not present (i.e. SDTM CE.CEOCCUR is neither Y nor N for the specified post-dose period for the event in question) but the group of solicited events (administration site or systemic) is marked as having occurred (i.e. SDTM CE.CEOCCUR=Y), all missing daily recordings will be given imputed values to allow them to contribute to the 'Any' rows but not to specific grade rows of the solicited event summary tables.

The following table shows how participants contribute to each category for a specific solicited event over the Day X to Day Y post-dose period:

Solicited event category	Participants included in the calculation of the numerator
Any	All participants with at least one occurrence of the adverse event at grade 1, grade 2, or grade 3 between Day X and Day Y or with the adverse event marked as present and at least one missing daily recording between Day X and Day Y
At least grade 1	All participants with at least one occurrence of the adverse event at grade 1, grade 2, or grade 3 between Day X and Day Y
At least grade 2	All participants with at least one occurrence of the adverse event at grade 2 or grade 3 between Day X and Day Y
At least grade 3	All participants with at least one occurrence of the adverse event at grade 3 between Day X and Day Y

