10.3.9. Assessment of intensity and toxicity

10.3.9.1. Assessment of intensity

The intensity of the following solicited events will be assessed as described:

Table 28 Intensity scales for solicited events in adults

Adults		
Event	Intensity grade	Parameter
Pain at administration site	0	None
	1	Mild: Any pain neither interfering with nor preventing normal everyday activities.
	2	Moderate: Painful when limb is moved and interferes with everyday activities.
	3	Severe: Significant pain at rest. Prevents normal everyday activities.
Erythema at administration site		Record greatest surface diameter in mm
Swelling at administration site		Record greatest surface diameter in mm
Temperature*		Record temperature in °C/°F (with 1 decimal)
Headache	0	Normal
	1	Mild: Headache that is easily tolerated
	2	Moderate: Headache that interferes with normal activity
	3	Severe: Headache that prevents normal activity
Fatigue	0	Normal
	1	Mild: Fatigue that is easily tolerated
	2	Moderate: Fatigue that interferes with normal activity
	3	Severe: Fatigue that prevents normal activity
Myalgia	0	Normal
	1	Mild: Myalgia that is easily tolerated
	2	Moderate: Myalgia that interferes with normal activity
	3	Severe: Myalgia that prevents normal activity
Arthralgia	0	Normal
	1	Mild: Arthralgia that is easily tolerated
	2	Moderate: Arthralgia that interferes with normal activity
* D. C. 1. O. 1 4.0 C. II 1 C. 11	3	Severe: Arthralgia that prevents normal activity

^{*} Refer to Section 1.3 for the definition of fever and the preferred location for temperature measurement.

The maximum intensity of local administration site erythema/swelling and fever will be scored at GSK as follows:

	Erythema/swelling	Fever
0:	≤ 20 mm	< 38.0°C (100.4°F)
1:	> 20 - ≤ 50 mm	≥ 38.0°C (100.4°F) - ≤ 38.5°C (101.3°F)
2:	> 50 - ≤ 100 mm	> 38.5°C (101.3°F) - ≤ 39.0°C (102.2°F)
3:	> 100 mm	> 39.0°C (102.2°F)

The investigator will assess the maximum intensity that occurred over the duration of the event for all unsolicited AEs (including SAEs) recorded during the study. The assessment will be based on the investigator's clinical judgment.

212496 (RSV OA=ADJ-004) Protocol Amendment 1 Final

The intensity should be assigned to 1 of the following categories:

1 (mild) = An AE which is easily tolerated by the participant, causing minimal discomfort and not interfering with everyday activities.

2 (moderate) = An AE which is sufficiently discomforting to interfere with

normal everyday activities.

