5.4.5. Additional considerations

- Compliance in completing solicited events information will be tabulated after each dose .
- The number and percentage of participants with at least one administration site event (solicited only), with at least one systemic event (solicited only) and with any solicited event during the 4-day follow-up period after each dose will be tabulated with exact 95% CI. The same computations will be done for Grade 3 AEs and for AEs resulting in a medically attended visit.
- The number of days with solicited events reported during the 4-day follow-up period will be tabulated for each solicited event, after each dose using descriptive statistics (mean, min, Q1, median, Q3, maximum).
- The number of each solicited events (any and Grade 3) that are ongoing beyond the 4-day follow-up period will be reported with the duration in days (mean, min, Q1, median, Q3, maximum).
- The list of solicited administration site and systemic events, and definition of intensity are described in Section 10.3.3 and 10.3.9.1 of the protocol.
- The number and percentage of participants with at least one report of SAE classified by the MedDRA Primary SOC, HLT and PTs and reported within 30 days following each vaccination will be tabulated with the exact 95% CI. The same tabulation will be presented for pIMDs.

The measurement of erythema/swelling (in mm) and fever (in °C/F) will be categorized as follows:

Grading	Erythema/swelling	Fever
0:	≤ 20 mm	< 38.0°C (100.4°F)
1:	> 20 - ≤ 50 mm	≥ 38.0°C(100.4°F) - ≤ 38.5°C(101.3°F)
2:	> 50 - ≤ 100 mm	> 38.5°C(101.3°F) - ≤ 39.0°C(102.2°F)
3:	> 100 mm	> 39.0°C(102.2°F)

Table 7Intensity grading scale for solicited events

Combined Solicited events and Unsolicited AEs

For clinicaltrials.gov and EudraCT posting purposes, a summary of combined solicited and unsolicited non-serious adverse events will be produced by System Organ Class and preferred terms and according to occurrence of each event.

Solicited events will be coded by MedDRA as per the following codes:

Solicited event	Lower level term code	Corresponding Lower level term decode
Pain	10022086	Injection site pain
Erythema	10022061	Injection site erythema
Swelling	10053425	Injection site swelling
Fever	10016558	Fever
Headache	10019211	Headache
Fatigue	10016256	Fatigue
Myalgia	10028411	Myalgia
Arthralgia	10003239	Arthralgia

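### For erythema and swelling, a reaction marked present but never recorded above 20 mm counts as 'Any' only if the diary has a missing day

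*SAP*

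**What the plan says.** SAP Amendment 3, section 10.1.2.3.1, sets the counting rules for paper diaries. A participant enters the 'Any' row for a solicited event by one of two routes. The first is "at least one occurrence of the adverse event at grade 1, grade 2, or grade 3" in the solicited period. The second is "or with the adverse event marked as present and at least one missing daily recording between Day X and Day Y", which asks for no grade. The accompanying bullet says that when the event is marked as having occurred, "any missing daily recordings will be given imputed values to allow them to contribute to the 'Any' rows but not to specific grade rows". When it is marked as not having occurred, "all daily measurements will be imputed as Grade 0", so a gap then changes nothing. The same table defines an 'At least grade 1' category that needs a recorded graded day.

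For erythema and swelling, Protocol Table 28 (section 10.3.9.1) gives no grade for the participant to choose; the instruction is "Record greatest surface diameter in mm". Grading comes afterwards: "The maximum intensity of local administration site erythema/swelling and fever will be scored at GSK as follows". Both that scale and SAP Table 7 (section 5.4.5) put 20 mm or less in Grade 0.

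SAP 5.4.4 commits to any-grade, Grade 3 and medically attended counts for each solicited event after each dose. It does not commit to showing the 'At least grade 1' row.

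**The concern.** For pain, headache, fatigue, myalgia and arthralgia, Grade 0 means none or normal. Marking the event present therefore implies at least Grade 1 on some day. If no graded day was recorded, the event must have fallen on the missing one, and counting it in 'Any' is coherent.

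Erythema and swelling break that link. Protocol Table 25 solicits both without a size threshold, so a visible 15 mm reaction can be marked present and still be Grade 0 on every day. Whether it reaches 'Any' then depends on whether a diary day is blank.

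Occurrence of each solicited event after each vaccination is a secondary endpoint, and readers will compare Dose 1 with the revaccinations. If diary completeness differs between doses, the 'any grade' rate for these two events can move with no change in the reactions. The rows for any solicited administration site event and for any solicited event (SAP 5.4.5) could inherit the effect, although a participant already counted for pain adds nothing there.

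**Working it through.** The plan states no figure for this rule, so there is none to reproduce. The check applies the rules to example diaries and then gives a scale under stated assumptions.

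**Step 1: apply the rules to erythema over the 4-day period.** Grade 0 is 20 mm or less (SAP Table 7); the row definitions are those of SAP 10.1.2.3.1.

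| Event marked | Recorded diameters, mm | 'Any' | 'At least grade 1' |
|---|---|---|---|
| Present | 15, 15, 10, 0 | No | No |
| Present | 15, 15, 10, missing | Yes | No |
| Not occurred | 15, 15, 10, missing | No | No |
| Present | 25, 15, 10, missing | Yes | Yes |

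The first two diaries agree on every day recorded in both, yet only the second is in 'Any'. The third shows that a gap alone does nothing: the event must also be marked present. The 'At least grade 1' column does not depend on the gap, and the same holds for the Grade 2 and Grade 3 rows.

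**Step 2: scale.** Let *s* be the proportion of participants whose only reaction is 20 mm or less and marked present, and *d* the chance that a given diary day is missing. Assume that gaps are independent between days and unrelated to the reaction, and that none of these participants exceeded 20 mm on the missing day.

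- Chance of at least one missing day in four: 1 − (1 − *d*)⁴
- Excess in 'Any': *s* × [1 − (1 − *d*)⁴]

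Both *s* and *d* are assumptions; neither is in the documents.

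| *d* | At least one missing day | Excess, *s* = 2% | *s* = 5% | *s* = 10% |
|---|---|---|---|---|
| 1% | 3.9% | 0.08 points | 0.20 | 0.39 |
| 2% | 7.8% | 0.16 | 0.39 | 0.78 |
| 5% | 18.5% | 0.37 | 0.93 | 1.85 |
| 10% | 34.4% | 0.69 | 1.72 | 3.44 |

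The range is about 0.1 to 3.4 percentage points. That is roughly 1 to 34 participants out of 990 in RSV_annual, or 0.3 to 11 out of 330 in RSV_flexible revaccination. If 5% truly exceed 20 mm, *s* is 10% and *d* is 2%, 'Any' becomes 0.05 + 0.10 × 0.0776 = 5.8% instead of 5.0%.

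**Step 3: between doses.** With *s* fixed at 10%, a rise in *d* from 1% after one dose to 5% after the next moves 'Any' by 0.10 × (0.1855 − 0.0394), about 1.5 points, with no change in the reactions.

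**The case against.** The strongest reply is that the missing day is unknown. A participant who affirmed the event and left a day blank may have exceeded 20 mm on that day, so counting that person is a conservative choice for a safety table. This stands to a degree: the two diaries match only on their recorded days, and a reader who infers that every gap-triggered case is a false positive goes further than the documents allow. The reply does not make the row consistent, though. A fully recorded 15 mm reaction on all four days is excluded, while 10, 8, missing, 0 mm is included.

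A second reply is that the problem needs reactions of 20 mm or less to be marked present, and the case report form and Study Procedures Manual are not available here. That is a real dependency. The protocol points towards it, with no size threshold, diameters recorded and grading done later by the sponsor, but does not settle it.

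A reader might also extend the point to fever, since Grade 0 there is a measured range too. The documents do not support that. Fever is defined as 38.0°C or more (Protocol 1.3 and 8.2.1.6). Fever marked present with no recorded day at that level implies fever on the missing day, just as for pain.

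Safeguards exist: diaries are collected and verified with the participant (Protocol 10.3.8), and compliance is tabulated after each dose (SAP 5.4.5). They may reduce or reveal gaps but leave the counting rule unchanged. Finally, all analyses are descriptive, so no hypothesis test or decision rule turns on this.

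**Conclusion.** The point holds for erythema and swelling only, and only where the event is marked present. For those two events, the 'any grade' row mixes reactions above 20 mm with reactions of any size that have a diary gap, and its composition can shift between doses with diary completeness.

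The size cannot be estimated from the documents. The illustrative excess of about 0.1 to 3 percentage points rests on assumed frequencies of small reactions and missing days, on independent gaps, and on no reaction above 20 mm falling on the missing day; if some did, the true excess is smaller. It also rests on small reactions being marked present.

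A reader might infer that severe reactogenicity is overstated. It is not: the grade-specific rows, including Grade 3, need a recorded grade.

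**What to change.** In SAP 10.1.2.3.1 and 5.4.4, specify for erythema and swelling, after each dose:

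- the 'At least grade 1' row (a recorded diameter above 20 mm), shown next to 'Any';
- a separate row for participants with the event marked present, no recorded day above 20 mm and at least one missing day.

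Both the threshold rate and the conservative rate can then be read, and no participant is lost. State also whether a reaction of 1 to 20 mm is to be marked present. Leave the missing-day rule unchanged for fever, pain and the other symptom-graded events.

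While editing, reconcile SAP 5.1.3, which says missing solicited measurements are not replaced, with the imputation in 10.1.2.3.1.

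The cost is a short SAP addition, a small programming change for two event terms, and one or two extra table rows. The threshold row alone may slightly understate the rate if a reaction above 20 mm fell only on the missing day; the separate row makes those participants visible.

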10.1.2.4. Unsolicited adverse events

Unsolicited AE summaries are including SAEs unless specified otherwise.

Missing severity, relationship with study vaccine, and outcome of unsolicited AEs will not be replaced and will appear as 'UNKNOWN' when displayed in a statistical output.

10.1.3. Data derivation

10.1.3.1. Age at first dose in years

When age at first dose is to be displayed in years, it will be calculated as the number of complete calendar years between the date of birth and the date of first dose. For example:

DOB = 10SEP1983, Date of first dose = 09SEP2018 -> Age = 34 years

DOB = 10SEP1983, Date of first dose = 10SEP2018 -> Age = 35 years

In this study, we will collect only the year of birth. The rules for handling missing day and/or month in the DOB are given in Section 10.1.2.1.

Since only the year of birth will be collected in the eCRF, there might be some discrepancies between the age computed using standard derivation rules and the age category used in SBIR for the minimization.

Therefore, for the analysis by age, the age categories defined in Table 4 will be determined according to the information entered in SBIR (variable AGEGRP in SDTM SUPPDM), except for "≥65 YOA" category which will be obtained using the derived age because this category is not used in SBIR for minimization

10.1.3.2. Temperature

Temperatures will be presented in degrees Celsius (°C). Temperatures reported in degrees Fahrenheit (°F) will be converted as follows:

Temperature (Celsius) = ((Temperature (Fahrenheit) - 32) x 5)/9

10.1.3.3. Numerical serology results

Numerical serology results will be derived from the content of IS.ISORRES in the SDTM dataset. For humoral assays with a specific cut-off, the following derivation rules apply:

IS.ISORRES	Derived value
"NEG", "-", or "(-)"	cut-off/2
"POS", "+", or "(+)"	cut-off
"< value" and value is <= assay cut-off	cut-off/2
"< value" and value is > assay cut-off	Value
"> value" and value is < assay cut-off	cut-off/2
"> value" and value is >= assay cut-off	Value
"value" and value is < cut-off	cut-off/2
"value" and value is >= cut-off and value is <=ULOQ	value
"value" and value is > ULOQ	ULOQ*
All other cases	Missing

*This rule will be used to compute descriptive statistics (GMTs, fold increase etc).

